(English) EQ-5D-5L Pdf

Health care utilisation questionnaire

Healthcare Usage Questionnaire

We would like to know how much use you have made of the health and social services over the last 3 months. If you are not exactly sure, we would rather have your best guess than no information at all.

Please answer every question, even if the answer is 'No'.

1) Over the last 3 months, if, and how many times, have you used any of the following:

Type of Service	No	Yes	If yes: Number of visits
GP		At home	
		In the surgery	
		On the phone	
Practice nurse		At home	
		In the surgery	
		On the phone	
Social worker		At home	
		In the facility	
		On the phone	
Visit at home from a community nurse or Dr			
Specialist community clinic –with consultant			
NHS Smoking Cessation clinic			
Other (describe)			

2) Hospital outpatient visit for breathing related issues

Episode*	Name of the hospital	Reason for appointment	Specialty of Department	Number of appointment*
1 st				
2 nd				
3 rd				
4 th				

*Episode means a visit or group of visits related to a particular problem. Please write down how many appointments you have had for each episode

3) Accident and Emergency for COPD / breathing issues

Episode	Name of the hospital	Reason for visit	Referral from
1 st			GP
			Outpatient
			Self-referral
2 nd			GP
			Outpatient
			Self-referral
3 rd			GP
			Outpatient
			Self-referral
4 th			GP
			Outpatient
			Self-referral

4) Hospital Inpatient for COPD / breathing and chest issues

Episode	Name of hospital	Ward Speciality	Reason for admission	No of nights*
1 st				
2 nd				
3 rd				
4 th				

*If you were treated as a day patient (day case), then please write 0 under "number of night"

5) Are you currently in paid employment?

No (please go to question 5b) Yes (please go to question 5a)

5a If yes, how many days have you been absent from work because of COPD in the last 3 months?
Please state how many days 5b If you are not employed:,

In the last 3 months have you had to stop work completely due to your COPD disease

No

Yes

6) Over the last 3 months has a relative or friend taken time off work to look after you?

No

Yes, how many days

7) In the last 3 months, approximately how much additional money have you spent on travel (taxi car park fees and public transportation because of your COPD disease)

None

Yes, I spent £ _____

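### The A&E table in the usage questionnaire does not say whether a row is one attendance or one problem and has no visit count, so A&E use may be understated and recorded inconsistently

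*Combined protocol and SAP*

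**What the plan says.** The questionnaire is in the Appendices and asks about the previous 3 months.

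- **Question 1** (GP, nurse, social worker and similar contacts) asks for a number of visits for each service.
- **Question 2**, "Hospital outpatient visit for breathing related issues", has four numbered rows headed Episode with an asterisk. The footnote reads "Episode means a visit or group of visits related to a particular problem" and goes on "Please write down how many appointments you have had for each episode". A matching column is headed "Number of appointment".
- **Question 3**, "Accident and Emergency for COPD / breathing issues", has four numbered rows headed Episode without an asterisk. Its columns are hospital, "Reason for visit" and referral source. None of them holds a quantity.
- **Question 4**, "Hospital Inpatient for COPD / breathing and chest issues", has four numbered rows headed Episode without an asterisk. Its columns include "Reason for admission" and nights, and a day case is to be entered as 0 nights. There is no column for the number of admissions.

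Utilisation is part of the primary objective (Objectives). Cost per QALY and healthcare cost per patient are listed under Primary Outcomes (Analysis Plan, item b). The section Analysis of Outcomes justifies the instrument, a modified CSRI, as a valid measure of how often services are used.

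**The concern.** The only definition of an episode on the form allows several visits to count as one, and it stands just above the A&E table. In Question 2 this does no harm, because the appointments column restores the count. In Question 3 the number of filled rows is the only measure of quantity. A patient who carries the definition forward will enter repeat attendances in one flare-up as a single row, while another patient with the same history may use several rows. The person entering the data cannot tell which reading was used, and the same patient could answer differently at baseline and at 3 months.

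At stake are the A&E count and its cost in analyses that the plan treats as primary. The documents name no records-based source from which the true count could be recovered. With 30 to 60 patients per group, a few frequent attenders can weigh heavily on a mean cost, and they are the patients with repeats to group.

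**Working it through.** The plan states no A&E rate and no number of visits per problem, so there is no figure of its own to reproduce. The check has two parts.

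**1. Reading the tables side by side**

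| Question | Row label | Definition attached | Quantity field |
|---|---|---|---|
| 1 Community contacts | Service | Not needed | Number of visits |
| 2 Outpatient | Episode, asterisk | Visit or group of visits | Number of appointments |
| 3 A&E | Episode, no asterisk | None | None |
| 4 Inpatient | Episode, no asterisk | None | Nights per row |

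Of the four questions, only Question 3 lacks a quantity field. In Question 4, two stays merged on one row still give the right bed-days if the nights are added together, but the form then shows one admission instead of two. Two day cases merged on one row show 0 nights and one entry, so nothing on the form reveals the second.

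**2. Possible size in Question 3 (all inputs assumed)**

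Let v be the mean number of A&E visits per problem and s the share of patients who apply the Question 2 definition. Assume these patients attend as often as the others. A patient who groups records 1 row for every v visits, so

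share of visits lost = s × (1 − 1/v).

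| v | s = 0 | s = 0.5 | s = 1 |
|---|---|---|---|
| 1.1 | 0% | 4.5% | 9.1% |
| 1.25 | 0% | 10.0% | 20.0% |
| 1.5 | 0% | 16.7% | 33.3% |
| 2 | 0% | 25.0% | 50.0% |

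For example, v = 2 and s = 0.5 give 0.5 × (1 − 1/2) = 25%. The A&E part of the cost falls by the same share if each attendance is costed alike. The effect on total cost cannot be worked out, because the documents contain no unit costs.

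**Four-row limit.** With X visits per patient, the loss is 1 − E[min(X, 4)]/E[X], again on assumed rates per 3 months:

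| Mean visits | Poisson | Negative binomial, dispersion 0.3 |
|---|---|---|
| 0.25 | 0.00% | 2.0% |
| 0.5 | 0.04% | 8.0% |
| 1 | 0.43% | 21.5% |

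The limit matters only if counts are strongly skewed.

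**The case against.** The strongest reply is that the layout of Question 3 already points to one row per attendance. The footnote is tied by its asterisk to Question 2 alone, and its instruction concerns appointments. Question 3 asks for the reason for a visit, in the singular, and for one referral source per row, which fits a group of visits poorly. Question 4 likewise describes a single stay. The questionnaires are administered at study visits, so staff could clear up a doubt. All of this stands as a reason why many patients may fill the table in correctly. It does not remove the ambiguity: the label is the same, nothing redefines it, and no written instruction tells patients or staff what a row is.

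Two stronger readings are tempting, and the documents do not support them.

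- **That the form defines A&E visits and admissions as groups, so repeats are lost.** The definition belongs to Question 2. For Questions 3 and 4 the form is silent, so repeats may be lost. For admissions, the nights column can preserve bed-days.
- **That 21% to 58% of A&E visits go unrecorded and a true rate ratio of 0.70 appears as 0.75 to 0.80.** The arithmetic is right for assumed means of 0.5 to 1.0 visits (ratio shift at 0.5), with Poisson counts or negative binomial counts with dispersion 0.5. But it requires every patient to merge all A&E visits in 3 months into one row. Even under the Question 2 definition, separate problems take separate rows. If grouping habits and visits per problem are alike in the two arms, both means shrink by the same factor and the ratio stays at 0.70. The absolute difference, which drives a cost comparison, would still shrink by that factor.

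**Conclusion.** The point holds as an ambiguity with a possible undercount. Question 3 reuses a term just defined as possibly several visits and gives neither a count column nor a one-row-per-visit rule. A&E counts and costs may therefore be understated and not comparable between patients. In Question 4 the exposure is narrower: the number of admissions and of grouped day cases. The four-row limit is secondary.

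The size runs from nil, if all patients use one row per visit, to 10% to 25% of A&E visits if half group them, or 20% to 50% if all do, at an assumed 1.25 to 2 visits per problem. The documents give nothing that would narrow this range, and they do not show that the comparison between arms is biased as a ratio. The case for acting is that the change is cheap and that grouped entries cannot be separated afterwards from the form.

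**What to change.** - In Question 3 replace the row label with *Visit*, and in Question 4 with *Admission*. Add to both: *one line for each time, even if for the same problem*.
- Above each of these tables add a total: *How many times in total in the last 3 months?* For Question 4, say that day cases are included. Take the analysed counts from these totals, which also cover events beyond the fourth row. Nights of a fifth or later admission would still need a continuation line.
- Keep the group-of-visits definition for Question 2 only, where the appointments column makes it workable.

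The cost is one extra item per table and the rewording of one appendix form, with no added visit or staff. The same revised form must be used at baseline and at follow-up, since a change between them would itself create a difference in recorded use.

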Long term Conditions (LTC) service within Solent NHS trust includes specialist services for patients with COPD, diabetes and cardiac disease. COPD carries a high symptom burden including mobility limitations and fear of acute episodes of breathlessness; often leading to decreased social interaction, and isolation. Evidence suggests that social interaction acts positively in terms of influencing wellbeing and living successfully with a LTC (Reeves 2014). Isolation has a negative impact on health in general and those with a long term condition in particular. It leads to low mood and an increasing inability to engage with self-care and self-management, and has physiological effects on health (Cacioppo, J 2004). Recent research which explores the nature of consultations with people with COPD suggests that opportunities for engagement with Self-Management Support (SMS) are often missed (Chatwin et al 2014). Moreover, social network connections might be a promising avenue for bringing into focus SMS options that have not previously been explored in professional patient encounters. The latter have been shown to have utility for the mobilisation of resources for self-management and for social involvement likely, to have an impact on self-management and health related outcomes.

Theories of Self-management are based around either the ability to manage a single clinical condition or the ability to manage everyday life; success in these is determined by the ability to fulfil 'normal' social roles and the ability to seek happiness in one's life. The element of social interaction forms the theoretical basis of disease management and health care navigation. For example, adult children are often considered as being pivotal to the social network by the person with the condition. However, the person with the condition is often reluctant to impose a burden of care on children and communicating support needs can be difficult to negotiate when it changes the parent/child relationship .The ability to recognise fractured networks are important when organising

and supporting care giving. However creating broader networks within personal trajectories of chronic illness can influence and support people in terms of daily living with a LTC, and support elements of weakness in existing networks.

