The main aim here is to increase long term health care management options in Solent NHS Trust by building social capacity to support self-management. The GENIE tool will be introduced into the COPD service to improve options for social groups and exercise when leaving a pulmonary rehabilitation group, or when clinically unable to participate in exercise.

- to build social networking awareness and the importance of utilising existing social resources in the professional and voluntary members of the COPD service,
- to use social network mapping techniques and preference elicitation to engage COPD patients in reflecting on their support preferences and needs, help them access further resources and knowledge
- Evaluate the success of the social mapping techniques (GENIE) in the COPD patient population
- Evaluate the cost benefit to both to patients and to the health service of the GENIE in the COPD patient population

Objectives

Primary objectives

Compare and evaluate the health care utilisation and quality of life (burden of disease) in COPD patients using GENIE alongside usual care after leaving the COPD service with those offered only a current practice discharge plan.

Secondary objectives

Compare and evaluate the change in health behaviours, in particular diet and lifestyle in COPD patients using GENIE alongside usual care after leaving the COPD service with those offered only a current practice discharge plan.

Observe and understand the uptake and utilisation of the GENIE recommendations by COPD patients.

Explore social complexities in the COPD population.

Implementation Design

[figure not shown]
This protocol is concerned with the implementation and evaluation of the GENIE tool in the community facilitated by the COPD team and the subsequent evaluation of the GENIE in direct comparison to usual clinical practice.

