Following the training, the participants will be given the tools required to roll out the intervention

- Paper and web-based concentric circles with typologies and support suggestions
- Guidebook on how to deliver GENIE
- Access to the database and website

Identification, enrolment and randomisation

[figure not shown]

Table of Events

	Consent and Randomisation	Pre – intervention data collection	12 weeks post intervention data collection (+/- 1 week)	Potential 1 year follow up phase
Consent form discussion and taking informed consent	x			
Randomisation (Block)	x			
EQ-5D		X	x	x
Health Care Utilisation Questionnaire		X	x	x
Socio-economic background / demographic data		X		
Gender		X		
Disease severity (FEV1)		X		
HEIQ (Self-management)		X	x	
Optional Health behaviour questionnaire		x	x	x
CAT		X	x	x
Gad-7 /		X	x	
PHQ-9		x	x	x
Uptake discussion / online survey			x	x

Quality Assurance

The delivery of the intervention will be taped in as many cases as consented to ensure that the intervention is delivered consistently by the research team to all patients. The tape recording is for quality assurance, and is not intended for research utilisation or publication.

Future work

The participants included in this initial 3 months of the study could be followed up again in 1 year (12 months) to ascertain longer term outcomes and longevity of connections made. This element could consist of a paper or online survey to understand the uptake rates of the social actives 1 year on, and further investigation into QOL, **healthcare use and the option of assessing health behaviours.** All participants would be given the option of continuing for a year, and therefore those who continue would be decided by participant preference to remain in the study.

Analysis Plan

Primary Outcomes

Descriptive statistics of the cohort,

Descriptive statistics of the cohort will be reported including but not limited to; age, gender, severity of disease then the analysis will be broken down into 5 distinct sections;

- a) Pre and post intervention cost utility analysis for the usual care group and the intervention group.
- b) Comparative group - pre and post cost utility analysis; calculated cost per QALY (quality adjusted life years) gained and cost of healthcare usage per patient– usual care group at 3 months after leaving the COPD service compared with the post intervention group 3 (+/- 1 week) months after leaving the COPD service, with significance.

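### The usage questionnaire counts community contacts for any cause but hospital care only for respiratory reasons, so the primary cost outcome is neither all-cause nor COPD-specific

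*Combined protocol and SAP*

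**What the plan says.** The Healthcare Usage Questionnaire in the Appendices opens without any limit on cause: "We would like to know how much use you have made of the health and social services over the last 3 months". Question 1 is equally open, "Over the last 3 months, if, and how many times, have you used any of the following", and lists GP, practice nurse, social worker, home visits, community clinic, smoking cessation and an open row for anything else.

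The three hospital questions are each restricted, in different words:

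- Question 2: "Hospital outpatient visit for breathing related issues"
- Question 3: "Accident and Emergency for COPD / breathing issues"
- Question 4: "Hospital Inpatient for COPD / breathing and chest issues"

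The primary objective (Objectives) is unrestricted: "Compare and evaluate the health care utilisation and quality of life (burden of disease) in COPD patients using GENIE". Under Analysis Plan, Primary Outcomes, item b) lists cost per QALY gained and "cost of healthcare usage per patient", again with no reference to cause. The Analysis of Outcomes section says that the economic analysis uses a modified CSRI tailored to COPD patients, and that EQ-5D assesses health status. The Table of Events lists one utilisation questionnaire and no extraction of hospital records.

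**The concern.** A cost outcome needs one perspective. The analyst can count all care whatever the cause, or care for the index disease only, but the items added together should follow the same rule. This form applies one rule to community contacts and another to hospital care. A respondent who follows it literally and is admitted after a fall reports no inpatient stay, while GP visits for the same fall are counted.

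The hospital filters also disagree with one another, since chest problems are mentioned only for inpatient care. A non-respiratory chest complaint could qualify if it led to admission but not if it was dealt with in A&E.

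A cost that mixes scopes would be divided by a QALY difference from EQ-5D, a general health measure. Any change in non-respiratory hospital use, favourable or not, would be invisible in a result labelled as healthcare cost. Episodes that the form never asks for cannot be recovered at analysis.

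**Working it through.** **Step 1. Is there a figure to reproduce?** No. The plan gives no unit costs, admission rates, expected EQ-5D difference or cost standard deviation. The check is one of scope, followed by an illustration of scale.

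**Step 2. Scope, side by side.**

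| Item | Limit on cause |
|---|---|
| Questionnaire introduction | none |
| Question 1, community contacts | none |
| Question 2, outpatient | breathing |
| Question 3, A&E | COPD or breathing |
| Question 4, inpatient and day case | COPD, breathing or chest |
| Primary objective | none |
| Item b), cost per patient and cost per QALY | none |
| EQ-5D | none (general health status) |

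Summing questions 1 to 4 does not give all-cause cost, because non-respiratory hospital care is not requested. It does not give COPD cost either, because question 1 includes unrelated contacts and has no reason column by which to remove them.

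**Step 3. Can the gap be filled from elsewhere?** The reason columns in questions 2 to 4 let staff screen episodes that were reported but do not bring back those left out. The open row in question 1 could hold such an episode, but nothing directs respondents to use it that way. No record review is described.

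**Step 4. Illustration of scale (assumed inputs).**

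- n = 30 or 60 patients per arm (from the recruitment paragraph of the protocol)
- Follow-up of 3 months = 0.25 year (from the protocol)
- A = cost of one unrecorded admission, £1,000 to £4,000 (assumed)
- dU = between-arm EQ-5D difference at 3 months, reached linearly, 0.03 to 0.10 (assumed)

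Shift in mean cost = A / n. QALY difference = 0.5 × dU × 0.25. Shift in cost per QALY = (A / n) / (0.5 × dU × 0.25), with one more unrecorded admission in one arm than in the other.

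QALY difference: 0.5 × 0.03 × 0.25 = 0.00375; 0.5 × 0.05 × 0.25 = 0.00625; 0.5 × 0.10 × 0.25 = 0.0125.

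| n per arm | A | dU | A / n | Shift in cost per QALY |
|---|---|---|---|---|
| 30 | £1,000 | 0.10 | £33.3 | £2,667 |
| 30 | £2,000 | 0.05 | £66.7 | £10,667 |
| 30 | £4,000 | 0.03 | £133.3 | £35,556 |
| 60 | £1,000 | 0.10 | £16.7 | £1,333 |
| 60 | £2,000 | 0.05 | £33.3 | £5,333 |
| 60 | £4,000 | 0.03 | £66.7 | £17,778 |

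For a positive QALY gain with GENIE, an admission missed in the GENIE arm makes the reported ratio too low, and one missed in the usual-care arm makes it too high.

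**The case against.** The best defence is that a disease-related scope was intended. The Analysis of Outcomes section says that the instrument was tailored to COPD patients, and the items on work absence, stopping work, travel and other spending (questions 5, 7 and 8) are tied to COPD. Costing hospital care by index disease is a recognised choice, and it keeps unrelated, highly variable admissions out of a small trial. This stands as evidence of some disease focus. It does not settle the matter, because no respiratory-only perspective is stated and question 1 does not follow one.

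Four stronger readings are tempting, and the documents do not support them.

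- *The comparison is biased between arms.* A reader might infer that unblinded patients would classify episodes differently by arm. Nothing shows this, and the form does not say who judges what is breathing-related; the protocol says only that questionnaires are administered. Under randomisation the omission is equal in expectation unless GENIE changes non-respiratory hospital use or its reporting.
- *The most expensive items are missing.* Respiratory outpatient, A&E and inpatient care is captured. Only the non-respiratory share is lost, and its size is unknown.
- *A cardiac admission would certainly be missed.* The reference to chest problems in question 4 may capture it.
- *The protocol predicts effects on non-respiratory hospital care.* The Introduction says of isolation that "It leads to low mood and an increasing inability to engage with self-care and self-management, and has physiological effects on health". That makes wider effects plausible, but it is general background and forecasts nothing about hospital use.

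It is also an inference that the appended form is the whole modified CSRI. The protocol says that medication use is measured, yet the form shown has no medication question.

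**Conclusion.** The mismatch of scope is clear from the wording and affects an outcome listed as primary. Followed literally, the form yields a cost that is neither all-cause nor COPD-specific. That cost understates total healthcare cost per patient whenever non-respiratory hospital care occurs, and it is blind to any effect of GENIE on such care. This rests on the appended form being the only source of utilisation data, which is how the Table of Events reads.

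How much is lost cannot be calculated from the documents. The illustrative shifts, about £2,700 to £35,600 per QALY with 30 per arm and £1,300 to £17,800 with 60, depend entirely on the assumed admission cost and EQ-5D difference. A reader might take them as evidence of bias. They show only how sensitive a 3-month cost per QALY is to a single event, in either direction, and a recorded unrelated admission would move an all-cause ratio just as far. The point is a cheap improvement to make before data are collected.

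**What to change.** Reword questions 2, 3 and 4 identically, so that each asks for every outpatient, A&E or inpatient episode for any reason, and add a breathing-related yes/no box beside the existing reason column. Use all-cause cost in items a) and b) of the Analysis Plan, which matches the outcome as stated, and report hospital cost limited to breathing-related episodes alongside it.

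If the sponsor intends a COPD-only perspective, say so in the Analysis Plan, use one filter across the hospital questions, and apply the same restriction to question 1.

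The cost is three reworded questions and a minor amendment. The form becomes slightly longer and all-cause cost will be more variable; the yes/no box keeps the narrower hospital result available.
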